### **6.3.7.2 Cessation of Clean Intermittent Catheterization**

CIC should be discontinued when both of the following criteria are fulfilled:

- the patient does not have any associated symptoms which in the opinion of the investigator require CIC
- the PVR urine volume is < 350 mL

These criteria can be met at any time after the start of CIC and do not need to be assessed only at a pre-scheduled visit. The date of discontinuation of CIC should be documented. If the investigator deems that CIC should not be discontinued even though the above criteria are fulfilled, then this must be documented and the reason given.

Upon discontinuing CIC, the patient will be seen for a follow-up visit 1 week later where the PVR urine volume, associated symptoms, central laboratory urine analysis, and culture/sensitivity will be re-assessed. The investigator will determine whether the patient can then be followed at regularly scheduled study visits or whether additional follow-up visits should occur based on PVR urine volume and/or associated symptoms.

### **6.3.8 Adverse Events of Urinary Retention and Residual Urine Volume**

Protocol-specific definitions for adverse events of urinary retention and residual urine volume are provided in [Section 9.1.2 Study-specific Definitions for Particular Adverse Events](#).

The investigator should use the information from the regular assessment of PVR urine volume and the need to catheterize for urinary retention/elevated PVR urine volume to assess the stop date of these adverse events.

### **6.3.9 Dipstick Reagent Strip Test (Urine Dipstick)**

The urine dipstick is used to identify a potential UTI (see below for definition of UTI adverse event) and to provide immediate information to the investigator. The investigator may initiate empirical treatment with antibiotics if deemed necessary, however, the required urine samples must also be sent to the central laboratory.

Urine dipstick tests are performed in conjunction with a central laboratory urine analysis and urine culture and sensitivity test.

Randomization/Day 1 Urine Dipstick Reagent Strip Test Results:

Patients with a positive dipstick test for nitrites or leukocyte esterase indicating a potential infection at Randomization/Day 1 must not receive any study treatment until results of the central laboratory urine analysis and urine culture/sensitivity test are obtained. If a bacterial infection is confirmed, the patient should be treated with antibiotics as determined by the investigator. The patient may return for a rescheduled Randomization/Day 1 visit (within 35 days of screening) and receive study treatment once a dipstick confirms a negative result for infection and all the 'Day of Treatment 1 Criteria' are fulfilled.

Treatment 2 Urine Dipstick Reagent Strip Test Results:

Patients with a positive dipstick test for nitrites or leukocyte esterase indicating a potential infection at the Treatment 2 visit, must not receive Treatment 2 until results from a central laboratory urinalysis and urine culture/sensitivity test are obtained. If a bacterial infection is confirmed, the patient should not receive Treatment 2, and the infection should be treated with antibiotics as determined by the investigator. The patient may return for Treatment 2 once a dipstick confirms a negative result for infection and all the 'Day of Treatment 2 Criteria' are fulfilled. Note: the qualification visit procedures do not need to be repeated (please refer to [Section 5.10.2 Day of Treatment 2 Criteria](#)).

### **6.3.10 Urinalysis, Culture and Sensitivity**

Urinalysis will be performed at all study visits (excluding clinic visit at Week 24) by a central laboratory; a urine culture and sensitivity test will also be performed when central laboratory urine results are suggestive of a UTI (positive leukocyte esterase, nitrites, blood and/or microscopic sediments such as white blood cells [WBCs], red blood cells [RBCs] and/or bacteria).

Note: unscheduled central laboratory urinalysis and urine culture tests are performed if the PVR urine volume value at any visit is  $\geq 200$  mL (see [Section 6.3.6](#) Full Bladder Volume and Post-void Residual Urine Volume).

### **6.3.10.1 Adverse Events of Urinary Tract Infection**

Please refer to [Section 9.1.2](#) for the study-specific definition of urinary tract infection adverse events.

If a patient reports a UTI to the investigator that was evaluated by a physician not at the investigative site (eg, primary care physician or emergency room), then all reasonable attempts will be made to obtain the confirmatory urine analysis and culture/sensitivity results. In such instances, the UTI should still be captured on the adverse event eCRF.

### **6.3.11 Pregnancy Test**

Urine pregnancy testing will be performed at the study site on women of childbearing potential at screening for Treatment 1 and the day of treatment visit for Treatment 1 and, if applicable, at the qualification visit for Treatment 2 and day of treatment visit for Treatment 2. A negative result is required prior to receiving study medication.

### **6.3.12 Screening Laboratory Tests**

At screening, prior to Treatment 1, blood samples will be drawn from all patients for analysis of the following laboratory tests to be performed by the central laboratory: complete blood count, creatinine, and blood urea nitrogen. All male patients will undergo a prostate-specific antigen test also performed by the central laboratory.

[REDACTED]

### **6.3.14 Treatment Benefit Scale (TBS)**

This single-item 4-point scale ([Attachment 12.6](#)) is used to assess the patient-reported benefit of treatment of OAB with respect to improvement or worsening of their condition ([Colman et al, 2008](#)).

## **6.4 Other Study Supplies**

The following will be provided by Allergan:

- e-Diary with electronic patient bladder diaries

The study sites will be responsible for providing the following supplies:

- prophylactic antibiotics required prior to study treatment
- sedation and anesthesia for use during study treatment
- sterile saline (or other appropriate sterile fluid) for bladder visualization during cystoscopic procedures and for reconstitution of study medication
- needles and syringes for reconstitution of study medication
- needles for cystoscopic injection
- sterile single-use catheters for CIC, if required
- flexible or rigid cystoscope with injection port
- ultrasound or bladder scan for PVR urine volume measurements
- refrigerator to store dry/reconstituted study medication at a temperature of 2 to 8°C, monitored by a calibrated temperature recorder and temperature log
- internet connection (high-speed connection) for eCRF completion

## **6.5 Summary of Methods of Data Collection**

An IWRS will be used to screen, randomize, terminate early, complete a study visit, complete the study participation, and manage study medication inventory. Data will be collected using eCRFs via a validated electronic data capture system (EDC). Source documents will be used and stored at the sites, and may include a patient's medical records, hospital charts, clinical charts, patient chart, copy of the EDC file, as well as the results of diagnostic tests such as laboratory tests and ultrasounds. The data will be transferred via secure server to Allergan.

## 7. Statistical Procedures

The statistical analysis will be conducted using all patients who have completed the study or exited the study prematurely. A detailed statistical analysis plan (SAP) will be finalized prior to the first database lock for interim analysis to provide further details regarding the definition of analysis variables and methodology to meet all study objectives.

### 7.1 Analysis Populations

Three populations will be used for the statistical analysis: Intent-to-treat (ITT), Modified intent-to-treat (mITT) and Safety.

**ITT Population:** The ITT Population will include all randomized patients. Demographics and baseline characteristics will be analyzed using the ITT Population. Patients will be grouped and analyzed according to their randomization assignment, regardless of the actual treatment received.

**mITT Population:** The mITT Population will include all randomized subjects who had at least one efficacy assessment at baseline and a postbaseline visit. Efficacy variables will be analyzed using the mITT Population. Subjects will be grouped and analyzed according to their randomization treatment assignment, regardless of the actual treatment received.

**Safety Population:** The safety population will include all patients who receive the study drug (BOTOX or placebo). All safety variables will be analyzed using the Safety Population. Patients will be grouped and summarized according to the treatment they actually received.

### 7.2 Collection and Derivation of Primary and Secondary Efficacy Assessments

#### 7.2.1 Primary Efficacy Variables

The primary efficacy endpoint is:

- Change from baseline in number of episodes of urinary incontinence at Week 12 as recorded by the patient in the 3-day bladder diary.

The following algorithms will be used for diary data conventions:

If there are no diary data (ie, none of the 3 diary days is a valid diary day), then the daily average frequency of urinary incontinence episodes will be considered as missing.

If a diary is completed for at least 1 day at any particular visit, then that patient's daily average frequency of urinary incontinence episodes in a 3-day period for that given visit will be estimated by using the daily average number of urinary incontinence episodes of the available days in the 3-day diary period.

A valid diary day is defined as a day in any of the three 24-hour periods with 2 or more urinary episodes of any type. For a valid diary day, if no incontinence episodes are recorded, the number of incontinence episodes on that day will be treated as zero. For an invalid diary day, both the number of incontinence episodes on that day will be treated as missing.

If the number of episodes of urinary incontinence at baseline is missing, it will be imputed using the median of all non-missing values regardless of treatment group at study baseline.

[figure not shown]
For each scheduled post-treatment visit, missing values for the primary efficacy variable will be imputed using the last observation carried forward (LOCF) approach. Additional details will be provided in the SAP.

[figure not shown]
### **7.2.2 Secondary Efficacy Variables**

There are 5 secondary efficacy variables as follows:

- Proportion of patients who achieve 100% reduction in urinary incontinence episodes (complete continence) from baseline (ie, baseline prior to Treatment 1).
- Change from baseline in daily average number of micturition episodes.
- Change from baseline in daily average number of urgency episodes
- Change from baseline in daily average number of nocturia episodes.
- Proportion of patients who have a positive treatment response on the TBS (score of either 1 or 2, representing 'greatly improved' or 'improved', respectively).

The derivation of the first 3 secondary endpoints above, recorded from the 3-day bladder diary at each visit, will follow the same algorithm as for the primary efficacy endpoint described in [Section 7.2.1](#).

### **7.3 Hypothesis and Methods of Analysis**

Continuous variables will be summarized using mean, standard deviation, median, minimum value, and maximum value.

Categorical variables will be summarized using frequency counts and percentages.

Data will be listed in patient listings.

Statistical tests for all efficacy endpoints will be 2-sided at significance level of 0.05.

No adjustment for the multiplicity of the endpoints will be performed.

Additional details of the statistical analyses, methods, and data conventions will be described in the SAP.

### 7.3.1 Primary Efficacy Analyses

The primary efficacy endpoint is the change from baseline at Week 12 after study treatment in the daily average number of episodes of urinary incontinence in the 3-day bladder diary period.

The primary efficacy analyses will be based on the mITT Population, with imputation of missing values as described above in [Section 7.2.1](#).

Let  $\mu_1, \mu_2$  be the true mean change from baseline at Week 12 in the daily average number of episodes of urinary incontinence for BOTOX 100 U and placebo, respectively.

The hypothesis of the primary analysis will be formulated as

H0:  $\mu_1 - \mu_2 = 0$  vs

HA:  $\mu_1 - \mu_2 \neq 0$ .

The hypothesis will be tested using an analysis of covariance (ANCOVA) model with treatment as a factor at 2 levels, and the number of UUI episodes reported at baseline ( $\leq 9$  versus  $> 9$  daily episodes, during the 3-day bladder diary at baseline) and baseline daily average number of episodes of incontinence as covariates. Least squares (LS) mean for each treatment and 95% confidence interval (CI) for  $\mu_1 - \mu_2$  will be calculated.

In addition, baseline daily average number of urinary incontinence episodes and daily average number of urinary incontinence episodes at Week 12 within each treatment will be compared using a paired t-test.

In addition to the analysis provided above at Week 12, the same analysis will be applied to all other scheduled visits.

[figure not shown]
### 7.3.2 Secondary Efficacy Analyses

The 5 secondary endpoints are listed in [Section 7.2.2](#).

The analysis of all secondary endpoints will be based on the mITT Population.

The first and the last secondary endpoints on the list are categorical variables, and they will be analyzed using a Cochran Mantel-Haenszel (CMH) test with the number of UUI episodes reported at baseline ( $\leq 9$  versus  $> 9$  daily episodes, during the 3-day bladder diary at baseline) as another categorical factor at each scheduled visit. Point estimate and the 95% CI for the odds ratio (BOTOX 100 U/placebo) will be calculated.

The second to the fourth secondary endpoints on the list are continuous variables. Each of the 3 continuous endpoints will be analyzed at each scheduled visit using an ANCOVA model with treatment as a factor and baseline value corresponding to the given endpoint and the number of UUI episodes reported at baseline ( $\leq 9$  versus  $> 9$  daily episodes, during the 3-day bladder diary at baseline) as covariates. A 95% CI for the LS mean difference of a given endpoint between the 2 treatments will be calculated. A paired t-test will be performed to compare the baseline value to a post-treatment value at each visit for each endpoint.

between the 2 treatments will be constructed. A paired t-test will be performed for the comparison between baseline and a post-treatment value at each visit for each endpoint.

The categorical endpoints will be analyzed using a CMH test with the number of UUI episodes reported at baseline ( $\leq 9$  versus  $> 9$  daily episodes, during the 3-day bladder diary at baseline) as another categorical factor at each visit. Point estimate and 95% CI for the odds ratio will be calculated for each endpoint at each visit.

The time-to-first-event endpoint will be analyzed using the Kaplan-Meier procedure for median time-to-request of re-treatment event by days (and weeks). Between-group comparisons of the 2 treatments will be performed using the log-rank test. A 95% CI for the median time-to-request of re-treatment for each treatment will be calculated.

### **7.3.4 Safety Analyses**

All safety analyses will be conducted on the safety population.

Descriptive statistics will be used to summarize safety endpoints which include adverse events, clinical laboratory (urine analysis), vital signs, PVR urine volume, physical examination, CIC use, concurrent procedures, and concomitant medications.

Adverse events will be coded using Medical Dictionary for Regulatory Activities (MedDRA, Version 19.0 or later). Adverse events will be summarized by primary system organ class and preferred term for each treatment. This summary will include all treatment-emergent adverse events (TEAEs) recorded from first dose of study treatment up to the post-treatment follow-up. Tables of fatal adverse events, SAEs, and adverse events leading to study discontinuation will be summarized by treatment. TEAEs by severity and relationship to study drug will be summarized by treatment.

Parameters for urine analysis will be summarized descriptively by treatment at each visit during the study. Shift tables will be provided for selected laboratory parameters.

Vital signs and PVR urine volume, will be summarized descriptively for each treatment by visit. Change from baseline in PVR urine volume (continuous variable) will also be performed.

Concurrent procedures and concomitant medications will be summarized descriptively for each treatment.

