### **9.1 Definitions**

#### **9.1.1 Adverse Event**

Any untoward medical occurrence in a patient or clinical investigation subject administered a pharmaceutical product and that does not necessarily have a causal relationship with this treatment. An adverse event can therefore be any unfavorable and unintended sign (including an abnormal laboratory finding), symptom, or disease temporally associated with the use of a medicinal (investigational) product, whether or not related to the medicinal (investigational) product. In addition, during the screening period, adverse events will be assessed regardless of the administration of a pharmaceutical product.

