1.1 Study Objectives and Design

1.1.1 Study Design

This is a multicenter, randomized, double-blind, placebo-controlled, parallel-group study to assess the safety and efficacy of a single treatment of BOTOX, administered using an alternative injection paradigm, followed by a second treatment (if applicable) with BOTOX in patients with overactive bladder (OAB) with urinary incontinence whose symptoms have not been adequately managed with an anticholinergic.

Following the screening period, patients meeting the study inclusion/exclusion criteria will be randomly assigned by an interactive web response system (IWRS) to 1 of 2 treatment arms (BOTOX 100 U or placebo) in a ratio of 2:1 (Botox 100 U: Placebo). A central randomization scheme will be utilized. The overall enrollment period is estimated to be 24 months.

One randomization number will be assigned to each patient prior to the first treatment and will be associated with one of the following treatment arms:

- Double-Blind Period

BOTOX 100 U

Placebo

- Open-Label Period

BOTOX 100 U (DB treatment)/BOTOX 100 U (OL treatment if qualified)

Placebo (DB treatment)/BOTOX 100 U (OL treatment if qualified)

Subjects will be eligible to receive a second treatment if all the predefined OL treatment criteria are met (see protocol [Section 5.10.2](#)). All eligible subjects will receive BOTOX 100 U for OL treatment.

Subjects will be followed regularly for safety and efficacy at post-treatment visits. Subjects will complete up to 2 treatments with a minimum study participation of 25 weeks (i.e., if subject requests a second treatment at Week 12 and qualifies for second treatment) and a maximum duration of 53 weeks (i.e., if a subject qualifies for OL treatment at Week 30, receives an injection at Week 34, and completes other study visits at the maximum allowable visit window).

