6.5 Adverse Events

Treatment-Emergent Adverse Events (TEAEs) are defined as those that begin on or after initiation of first dose of study treatment. For re-treated subjects, the TEAEs started on or after the initiation of DB treatment and before the initiation of OL treatment will be assigned to double-blind period. The TEAEs started on or after the initiation of OL treatment will be assigned to open-label period. Refer to [Table 7](#) for the classification of TEAEs by treatment period as:

- Double-blind period
- Open-label period

Table 7: Classification of TEAEs

Subjects not re-treated:

TEAE Start Date/Time	TEAE Classification
DB Treatment start date/time <= AE start date/time	Double-Blind period

Subjects re-treated:

TEAE Start Date/Time	TEAE Classification
DB Treatment start date/time <= AE start date/time < OL Treatment start date/time	Double-Blind period
AE start date/time >= OL Treatment start date/time	Open-Label period

Adverse events will be classified by type, incidence, severity, and causality. The overall incidence of AEs will be summarized using the MedDRA coding system and classified by SOC, PT, and treatment group.

An overall summary table will present the number of events and the incidence of subjects having at least one event in the following categories:

- TEAEs
- TEAEs indicated as serious (SAEs)
- TEAEs leading to study discontinuation
- TEAEs leading to death
- TEAEs related to study drug
- Serious TEAEs related to study drug
- Possible distant spread of toxin (PDSOT) TEAEs (refer to [Section 6.5.2](#))
- TEAEs of urinary retention (Refer to [Section 6.5.1](#))
- TEAEs of residual urine volume (Refer to [Section 6.5.1](#))
- TEAEs of urinary tract infection (Refer to [Section 6.5.1](#))
 - TEAEs of asymptomatic urinary tract infection
 - TEAEs of symptomatic urinary tract infection

Tabulation (using counts and percentages) of TEAEs classified by SOC and PT will be provided. In addition, Tabulation of TEAEs classified by SOC and PT will be provided for each of the following:

- Serious TEAEs
- Treatment-Related Serious TEAEs
- TEAEs leading to study discontinuation
- Treatment-related TEAEs leading to study discontinuation

Tabulation of TEAEs classified by PT will be provided for each of the following:

- TEAEs
- Serious TEAEs
- TEAEs by maximum severity
 - Subjects with multiple TEAEs with the same PT will be summarized at the maximum severity and counted one time for that PT.
- TEAEs related to study drug

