- TEAEs leading to death

When reporting the number of TEAEs, if the same TEAE occurs for a subject on multiple occasions the event will be counted once for each occurrence.

All adverse events and related details will be listed by treatment group and subject. Non-treatment-emergent events will be identified in all listings, but not included in summaries.

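### SAP 6.5 classifies adverse events by start date only, so worsening after the open-label injection can be tabulated in the double-blind period

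*Protocol*

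**What the plan says.** Protocol 7.3.4 sets the scope of the main adverse event table: "This summary will include all treatment-emergent adverse events (TEAEs) recorded from first dose of study treatment up to the post-treatment follow-up". The protocol does not define treatment-emergent. SAP 6.5 does: "Treatment-Emergent Adverse Events (TEAEs) are defined as those that begin on or after initiation of first dose of study treatment".

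For retreated patients, the text above SAP Table 7 splits events between periods by onset: "the TEAEs started on or after the initiation of DB treatment and before the initiation of OL treatment will be assigned to double-blind period", and "The TEAEs started on or after the initiation of OL treatment will be assigned to open-label period". Table 7 repeats this using start date and time only. Events that fail the definition go to listings: "Non-treatment-emergent events will be identified in all listings, but not included in summaries".

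For the severity table the SAP says: "Subjects with multiple TEAEs with the same PT will be summarized at the maximum severity and counted one time for that PT". It does not say in which period the maximum must have been reached.

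Every second injection is BOTOX 100 U. One of the two open-label sequences in SAP 1.1.1 is therefore "Placebo (DB treatment)/BOTOX 100 U (OL treatment if qualified").

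**The concern.** An adverse event record can run across the second injection. The SAP recognises this for medications: Table 6 has rows that place a medication spanning both periods in both. Adverse events have no equivalent rule. Their period is fixed on the day they start, whatever happens later.

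Suppose a patient has a mild event in the double-blind period, receives open-label BOTOX, and the event then becomes severe or serious. If the site updates the existing record, the later grade is attached to a double-blind event. It appears in the double-blind severity or seriousness tables under the first treatment, and the open-label tables show nothing for it.

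Safety is part of the primary objective (Protocol 2.1), and an acceptable or better safety profile is a stated hypothesis (Protocol 2.2). SAP Section 6 rules out inferential safety comparisons, so the descriptive tables carry the whole safety result.

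The definition also affects events already present before the first dose that worsen after it. They are not treatment-emergent and stay out of the summaries.

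**Working it through.** **1. The rule as written.** Let A be the event start, D the first injection, O the open-label injection and W the date of worsening.

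- A < D: not treatment-emergent, listings only.
- D ≤ A < O: double-blind period.
- A ≥ O: open-label period.

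W does not enter the rule.

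**2. Test cases** (illustrative dates: D = 10 January, O = 20 April).

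| Start | Worsens or becomes serious | Table 7 as written | If W counted as an onset |
|---|---|---|---|
| 9 January | 17 January | listings only | double-blind |
| 21 March (Week 10) | 27 April | double-blind | open-label |
| 25 April | any later date | open-label | open-label |

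The second row is the main problem and the first row the smaller one. An event that starts and worsens within one period is classified correctly.

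**3. Which tables move.** The overall double-blind incidence does not change, because the event was already counted there. The double-blind entries for maximum severity and serious events change. The open-label tables lose the patient, unless that patient has another open-label event in the same category.

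**4. Size per patient.** At least 114 patients are to be randomised 2:1 (Protocol 4.1), which gives 76 BOTOX and 38 placebo. If all are treated:

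- placebo double-blind column: 1/38 = 2.6 percentage points per misplaced patient (1/34 = 2.9 at the Week 12 target of 34);
- BOTOX double-blind column: 1/76 = 1.3 points (1/68 = 1.5 at the target of 68).

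**5. Effect on the comparison.** Let r be the proportion of an arm that is retreated and w the proportion of those whose ongoing event worsens into the category. Each double-blind column rises by r × w, and the BOTOX-minus-placebo difference changes by r(BOTOX) × w(BOTOX) − r(placebo) × w(placebo).

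The documents give neither r nor w. As an assumption only, take r = 0.60 and w = 0.05 to 0.10 in both arms:

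- placebo: 38 × 0.60 = 22.8 retreated; 22.8 × 0.05 = 1.1 to 22.8 × 0.10 = 2.3 patients;
- BOTOX: 76 × 0.60 = 45.6 retreated; 45.6 × 0.05 = 2.3 to 45.6 × 0.10 = 4.6 patients;
- both columns rise by 0.60 × 0.05 = 3 to 0.60 × 0.10 = 6 points, and the difference does not change.

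The open-label columns are short by up to w, which only restates the assumption.

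**6. Which events can be ongoing at Treatment 2.** Protocol 5.10.1 requires a residual volume below 200 mL at qualification. Protocol 5.10.2 requires no urinary tract infection and a negative dipstick on the day of treatment. A retention event needs at least 200 mL plus catheterisation (Protocol 9.1.2). Active retention and urinary tract infection are therefore largely filtered out, and the problem chiefly concerns other ongoing events.

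**7. Which report is affected.** The topline covers the first 12 weeks after Treatment 1 (Protocol 7.6, SAP Section 7), and Treatment 2 may not be given before 12 weeks (Protocol 5.6.1). The final report carries the problem. The topline is only mostly clear of it: patients enrolled early may already have had Treatment 2 at the data cut, and the documents do not say whether severity is taken as at Week 12.

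**The case against.** The strongest objection is that the harm depends on a recording practice the documents do not describe. If sites open a new record when an event worsens, Table 7 works and the problem largely disappears. Such an instruction may exist: the visit schedule is blacked out, the amendment summary shows that its footnotes carried adverse event recording instructions, and eCRF completion guidance is not part of these documents. The SAP also allows several records of one preferred term per patient. This stands as a condition on the finding. It does not remove the need for a rule, because the tables should not depend on a convention the SAP leaves unstated.

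A reader might infer that the rule favours BOTOX by moving its harm into the placebo column. The documents do not support that. Worsening after a second BOTOX injection in a patient first given BOTOX is charged to the BOTOX double-blind column by the same rule. A net bias needs unequal rates, and the protocol points both ways. Its hypothesis of longer effect than placebo (2.2) predicts more or earlier placebo retreatment. Its Phase III background (Section 1) reports more local urinary events after BOTOX, which could leave more events open in that arm.

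Nor are serious events lost: all adverse events and all serious events are listed (SAP 6.5, 6.6). They are misplaced in the summaries.

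The pre-dose branch is small. Events go on the eCRF only from randomisation (Protocol 9.2), and Treatment 1 follows randomisation on Day 1. Screening events are assessed ("In addition, during the screening period, adverse events will be assessed regardless of the administration of a pharmaceutical product"), but those before randomisation are required only in source documents. A flare of a condition in the medical history may be entered as a new event. Some relevance remains: dry mouth and constipation are on the distant-spread list (SAP Table 8), and the protocol names both as side effects of the oral medicines these patients have used.

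**Conclusion.** The point holds as a gap in the classification rule, conditional on worsening being kept on its original record. Under that condition, open-label harm is understated in both sequences, and both double-blind columns of the final report can show severity or seriousness that arose after open-label BOTOX. The size is 2.6 points per placebo patient and 1.3 points per BOTOX patient in a severe or serious category. No total can be computed, because the documents give no rate of events ongoing at Treatment 2 or of their worsening. A bias in the between-arm difference, in either direction, is not shown. Retention and urinary tract infection are mostly outside the problem, the 12-week topline is mostly unaffected, and the exclusion of pre-dose events that worsen is a minor addition. The change is still worth making: it is cheap, and the safety conclusions rest on these descriptive tables.

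**What to change.** In SAP 6.5 and Table 7, define a treatment-emergent event as one that begins, increases in severity or becomes serious on or after an injection. State that such worsening is entered as a new adverse event record with its own onset date, and assign the period by that date. Ask sites for a complete date on these records, because SAP 2.3.2.1 imputes partial onset dates against the first injection only. Give the same convention in the eCRF guidance and refer to the definition from Protocol 7.3.4.

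SAP Section 1 allows revision before database hard lock. If records can no longer be changed, flag the adverse events ongoing at Treatment 2 and tabulate them separately by first treatment, with their later severity and seriousness.

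The cost is a few lines of SAP text, one line of site guidance, a few more adverse event records, and slightly higher treatment-emergent counts.
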